1.2 Investigational Device (Attachments A, B, C, D)

Bard™ Soft Mesh – is a light weight, woven, large open pore mesh made of polypropylene. It is an FDA approved product indicated for use in the reconstruction of soft tissue defects.

1.3 Clinical Data to Date

Multiple clinical studies have been conducted regarding implantation of mesh to reinforce abdominal wall defects and this is widely accepted among surgeons who treat hernias.^{16,17,30} Light weight polypropylene mesh, specifically implanted in the identical anatomical position as proposed by this study has been studied extensively in the treatment of ventral hernias and found to be safe and effective.^{23,24,31,32,41} Furthermore, a large scale, multiple institution trial using this specific mesh, and ones of similar design and construction marketed by other manufacturers, implanted in the same anatomic location under the same levels of wound contamination found acceptable infection and hernia recurrence outcomes.²³

1.3.1 Safety Events

The previously referenced trial reported an overall 31% incidence of surgical site occurrences (SSO), which were defined as any surgical infection, wound dehiscence, wound breakdown, enterocutaneous fistula, seroma/hematoma formation, wound cellulitis, suture abscess, or nonhealing wound as described by the Ventral Hernia Working Group.⁴² The criteria for 30-day SSI was taken directly from the CDC criteria and was categorized into superficial, deep, and organ space infections. This included 7% wound dehiscence rate, 5% incidence of seroma or hematoma, 4% wound cellulitis rate, and a 1% enterocutaneous fistula rate. The SSI rate was (14%) where S-SSI was 8%, D-SSI was 3%, and O-SSI was 3%. In their cohort, only 4% of patients required mesh removal.²³ These findings are consistent with other reports of similar studies.^{26,27}

1.4 Risk/Benefits

The primary concern is for surgical site occurrences. In the absence of mesh, the incidence of infection in ileostomy closures is estimated between 6 and 18%.⁴³⁻⁴⁵ This rate is minimized with the use of a purse string skin closure with iodine impregnated gauze packing vs partial closure with an open ended drain (Penrose type) or primary skin closure.⁴⁶ Prospective trial data estimates the overall incidence of infections when bioabsorbable mesh is placed in Class II and III ventral hernia repairs at 18%. None required mesh explantation and all wounds eventually healed.²⁷ Other reports of macroporous polypropylene mesh in clean-contaminated and contaminated wounds suggest an infection rate of 7.1% for clean contaminated and 19% for contaminated cases.²³ Surgical site occurrences will be treated on an individual patient basis determined by the clinical consequences of the occurrence. Infection may potentially be treated with antibiotics, local wound care, operative debridement, radiographically guided drainage procedures, vacuum assisted wound closure devices, or mesh removal at the discretion of the study team. Other potential adverse events are those inherent to intestinal surgery; anastomotic leak, peritoneal abscess formation, bowel obstruction, or ileus, in addition to the risks associated with general anesthesia.

2 Study Objectives

Primary Objective: To validate the technical procedure of mesh implantation at the time of ileostomy closure and preliminarily determine the incidence of surgical site occurrences (particularly those requiring intervention) compared to standard ileostomy closure technique.

Secondary Objective #1: Measure and compare quality of life scores for aspects related to the procedure to those related to bowel function.

Secondary Objective #2: To evaluate the process for longitudinally monitoring for the occurrence of hernia at site of stoma closure. We will evaluate our study protocol for the feasibility of performing a larger trial by measuring recruitment, retention of patients, adherence to the study protocol, and process assessment.

By the completion of this pilot study, our expected outcomes are to have demonstrated a high level of procedural fidelity among the operating surgeons of the modified ostomy closure technique and comparable costs to the standard procedure as well as greater than 80% recruitment and retention of eligible participants, and greater than 90% adherence to the study protocol. We also expect to preliminarily demonstrate safety and similar quality of life compared to historical controls on short term follow-up. These results are expected to inform development of an appropriately powered, multiple center, randomized controlled trial comparing the effectiveness of our novel modification of ostomy closure technique to the standard technique.

3 Study Design

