12	PUBLICATION PLAN.....	12
13	REFERENCES.....	13
14	ATTACHMENTS.....	15

List of Abbreviations

CCRC – Clinical Cancer Review Committee
DSMAC – Data Safety Monitoring and Accrual Committee
mL - Milliliter
MRSA – Methicillin-resistant Staphylococcus aureus
NCCC – Norris Cotton Cancer Center
NCCN – National Comprehensive Cancer Network
SSI – Surgical Site Infection
S-SSI - Superficial surgical site infection
D-SSI – Deep surgical site infection
O-SSI – Organ space surgical site infection
SCIP – Surgical Care Improvement Project
PDS – Polydioxanone
SSO – Surgical Site Occurance

Study Summary

Title	Stoma Closure and Reinforcement Trial (SCAR) – Pilot Study
Short Title	SCAR Trial
Protocol Number	1
Phase	Pilot feasibility
Methodology	Open Label
Study Duration	The study is estimated to last 5 years
Study Center(s)	Single center – Dartmouth Hitchcock Medical Center
Objectives	
 1. To perform a pilot study to validate the mesh implantation procedure at the time of ileostomy closure. 2. To evaluate patient satisfaction and resource utilization associated with the procedure. 3. To prospectively evaluate the cohort for evidence of hernia formation at the previous stoma site. 4. Use data from this trial to design an appropriately powered, multi-center, prospective randomized, controlled trial of mesh reinforcement of ileostomy closures.
Number of Subjects	20
Diagnosis and Main Inclusion Criteria	
 1. Left sided colon or rectal cancer treated with resection and diverting loop ileostomy, with or without neoadjuvant or adjuvant therapy. 2. Age > 18years 3. Patient is undergoing elective closure of diverting loop ileostomy
Study Product, Dose, Route, Regimen	Bard™ Soft Mesh (Bard Davol, Inc): large pore, open weave, monofilament polypropylene mesh.
Duration of administration	The mesh would be implanted as a reinforcement of the stoma closure on a permanent basis. The mesh is not intended to be removed.
Reference therapy	Standard procedure for ileostomy closure
Statistical Methodology	No power calculation is necessary for this study since it is a pilot study. The results will be used to calculate power for future investigations.

1 Introduction

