3.1 General Design

This is a pilot study evaluating the feasibility of a novel modification to an established surgical procedure. The three operating surgeons are faculty members of the Division of Colon and Rectal Surgery in the Department of Surgery at DHMC. All radiographs will be reviewed by a single faculty of the Department of Radiology. We will use a modified Simon Two stage approach, the first phase will include five patients treated and followed sequentially. If there are 1 or fewer major wound occurrences (those requiring return to the operating room) then the study will proceed to the second phase which will include a total of 15 patients followed concurrently.

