4.4.2 Data Collection and Follow-up for Withdrawn Subjects

Data related to the time period of the subject's participation will be included in the analysis of the treatment effect. Should a subject be withdrawn from the study for any reason, survival data will be maintained in accordance with the guidelines for follow-up prescribed by the NCCN.

5 Study Procedures

5.1 Encounter 1

Patients will be assessed for ileostomy closure based upon completion of therapy after primary resection of their malignancy. Appropriate candidates will be determined at the operating surgeon's discretion based on customary evaluation of clinical status. The informed consent process will be initiated and the patient recruited into the study.

5.2 Encounter 2

This encounter is the operative procedure. The procedure for closing the ileostomy (i.e. bowel anastomosis) will be at the discretion of the surgeon, provided it is performed through the ileostomy site without additional laparotomy incisions. In accordance with SCIP guidelines, pre-operative intravenous antibiotic and subcutaneous pharmacologic venous thromboembolism prophylaxis will be administered. Patients with a history of MRSA infection will also receive a dose of intravenous vancomycin prior to the procedure.

The abdominal wall reconstruction portion of the procedure will be standardized to ensure consistency between surgeons. The posterior rectus sheath is closed with native tissue either primarily, using hernia sac if present, or bridged with Vicryl-type mesh and a quickly absorbing suture material. This is done to isolate the mesh from the peritoneal cavity. The retrorectus plane is developed using electrocautery and blunt dissection to provide adequate placement of mesh such that it overlaps the posterior sheath defect by a minimum of 3cm on all sides. The mesh is placed in this plane and secured in place with slowly absorbable monofilament (0-PDS preferred) sutures placed through the anterior fascia or with application of fibrin sealant at the surgeon's discretion. This space is then irrigated with

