6.1 Sample Size Determination

6.2 This is a pilot study and therefore the anticipated number of patients included (20) represents an attainable number within the planned study period (1 year) based on the clinical volume of our group. Our group treats approximately 35-40 patients per year who would likely meet inclusion criteria for this trial. We estimate a cohort of 200 patients in a randomized trial will be required to demonstrate superiority of the technique, and a 10% sample of that cohort will be sufficient provide preliminary safety data as well as to demonstrate feasibility of a future trial.

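### The pilot's recruitment rate measures acceptance of mesh, not of random allocation, so it cannot by itself show that a randomised trial is feasible

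*Combined protocol and SAP*

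**What the plan says.** Secondary Objective #2 (section 2) sets the feasibility task: "We will evaluate our study protocol for the feasibility of performing a larger trial by measuring recruitment, retention of patients", followed by adherence and process assessment. The expected outcomes later in section 2 include "greater than 80% recruitment and retention of eligible participants". Section 6.2 justifies the pilot's 20 patients as a tenth of an estimated 200-patient randomised trial, enough for preliminary safety data "as well as to demonstrate feasibility of a future trial".

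The trial being prepared is randomised. Objective 4 of the Study Summary reads "Use data from this trial to design an appropriately powered, multi-center, prospective randomized, controlled trial of mesh reinforcement of ileostomy closures", and section 2 describes a "multiple center, randomized controlled trial comparing the effectiveness of our novel modification of ostomy closure technique to the standard technique".

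The pilot itself has no allocation step. In section 3.1, "the first phase will include five patients treated and followed sequentially", with 15 more to follow. At Encounter 1 (section 5.1), "The informed consent process will be initiated and the patient recruited into the study"; Encounter 2 (section 5.2) is the mesh operation. Section 6.3 takes its comparator from an existing institutional database, and section 6.4 analyses those who had the study procedure.

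**The concern.** Recruitment is a feasibility measure for a later trial whose consent question differs from the pilot's. A pilot patient agrees to have mesh and to attend study follow-up. A patient in the later trial must agree that chance decides between mesh and standard closure, and the surgeon must be content with either result. A patient who wants mesh may accept the first and refuse the second, and the pilot cannot tell such a patient from one who would accept both.

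The protocol's own background gives reason to ask. Section 1.1 argues that closing a stoma site resembles a hernia repair and that suture repair alone is poorly supported there. The same section reports the historical worry about mesh in contaminated fields, and section 1.4 names surgical site occurrences as the primary concern. Preferences in either direction are therefore plausible. At stake is the planning of the next trial: if pilot recruitment is carried over as the expected randomisation rate, the number of centres or the accrual time could be set wrongly.

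**Working it through.** **1. The plan's own figure.** Section 6.2: 0.10 × 200 = 20. This reproduces.

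**2. The 200.** No alpha, power or dropout is stated. Assume two-sided 5%, 80% power, 1:1 allocation and no dropout. Take a control hernia rate of one third (section 1.1) and a 50% reduction (section 6.3), that is 1/3 against 1/6. The mean rate is 0.25 and the difference 1/6.

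n per arm = [1.96 × √(2 × 0.25 × 0.75) + 0.842 × √(1/3 × 2/3 + 1/6 × 5/6)]² / (1/6)² = (1.200 + 0.506)² / 0.0278 ≈ 105, or 210 in total.

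So 200 is plausible but cannot be verified from stated inputs. The present point does not depend on it.

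**3. What each recruitment rate measures.**

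| | Pilot | Later trial |
|---|---|---|
| Treatment offered | Mesh for all (5.2, 6.4) | Mesh or standard closure by chance (Study Summary, 2) |
| Comparator | Historical controls (6.3) | Concurrent randomised arm |
| Consent covers | Mesh and follow-up | Allocation by chance and follow-up |

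Two entries might suggest a second arm. The Study Summary lists standard closure as reference therapy, and section 5.3 has a radiologist blinded to the presence of mesh. Neither sets up a concurrent group.

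**4. Precision of the pilot's rate.** To exceed 80% with 20 enrolled, at most 24 can have been approached: 20/24 = 83%, exact 95% CI 63% to 95%. The interval is wide, and it concerns acceptance of certain mesh.

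**5. How much the unmeasured rate could matter.** Inputs from section 6.2: 200 patients, and 35-40 likely eligible a year at this centre. The acceptance rate a is assumed. Site-years = 200 / (eligible per year × a).

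| Assumed a | Patients to approach (200/a) | At 40 a year | At 35 a year |
|---|---|---|---|
| 80% | 250 | 6.3 | 7.1 |
| 70% | 286 | 7.1 | 8.2 |
| 50% | 400 | 10.0 | 11.4 |

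The 80% row uses the plan's own recruitment figure as if it carried over to randomisation. If true acceptance were 50%, the site-years would rise by a factor of 0.80/0.50 = 1.6; at 70%, by 0.80/0.70 = 1.14. The pilot's recruitment rate does not say which row applies.

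**6. Precision of a direct question.** With 25 patients approached (assumed) and 12 answering yes, 12/25 = 48%, exact 95% CI 28% to 69%. This is as imprecise as the pilot's own rate, but it concerns the relevant quantity.

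**The case against.** The strongest reply is that a staged, mesh-only pilot is a legitimate first step, and that its primary endpoint is the procedure and 30-day wound occurrences. Recruitment is one of four measures inside the second secondary objective. Most forward-looking statements are modest: the data are to inform or help design the next trial. Acceptance of randomisation could be studied later, at the centres that will take part. All of that stands, and nothing here asks the pilot to randomise.

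A reader might infer that the pilot says nothing about feasibility of the later trial. The documents do not support that. It yields the number of eligible patients, acceptance of mesh with study ultrasounds and questionnaires, retention, adherence and procedural fidelity. Willingness to have mesh is also generally a condition of entering a trial with a mesh arm, so refusals carry information.

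A reader might also take the 80% figure as a rule for proceeding. It is listed as an expected outcome, and no section makes it a go/no-go criterion.

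Nor does the illustration show that the later trial would fail to accrue. The acceptance rates are assumed and the trial is multicentre: 11.4 site-years over five similar centres (also assumed) is 11.4 / 5 ≈ 2.3 years.

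What survives is section 6.2, which claims that the sample will demonstrate feasibility in the same sentence that describes the later trial as randomised. Recruitment to a mesh-only cohort cannot carry that claim.

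**Conclusion.** The point holds in a limited form, as a cheap improvement. The pilot's recruitment rate estimates acceptance of certain mesh and its follow-up. It leaves acceptance of random allocation unmeasured, among patients and surgeons alike, and so cannot by itself demonstrate feasibility of a randomised trial. The conclusion rests on the design as written: no allocation step, no concurrent arm and no record of willingness to be randomised.

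Its size cannot be estimated from the documents. Over assumed acceptance of 80% down to 50%, the effort to randomise 200 runs from about 6.3 to 11.4 site-years. The pilot rate should not be treated as a sure upper or lower bound on randomised recruitment. No pilot endpoint, analysis or safety decision is affected.

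**What to change.** 1. In sections 2 and 6.2, limit the conclusion drawn from recruitment to acceptance of the mesh procedure and its follow-up. Keep eligible volume, retention, adherence and procedural fidelity as feasibility measures.
2. At Encounter 1 (section 5.1), record for every eligible patient approached, including those who decline, whether they would have agreed to have mesh or standard closure decided by chance: yes, no or unsure, with the reason.
3. Put the same question to the three operating surgeons and report their answers descriptively.
4. Report the patient proportion answering yes, with its denominator and an exact 95% CI, as one rough guide for planning the next trial.

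The cost is one screening question with IRB-approved wording that also covers decliners, a short question to three surgeons, and two edited sentences. The drawback is that the answer is hypothetical and, with about 25 respondents, imprecise (28% to 69% in the example). It should not be used as the accrual assumption on its own. Decliners' answers cannot readily be recovered later, so the question is best in place before the first patient is approached.

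### Does enrolling 20 of the 35-40 patients seen each year put the target of more than 80% recruitment out of reach?

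*Combined protocol and SAP*

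**What the plan says.** Secondary Objective #2 in section 2 says that recruitment, retention, adherence and process will be measured to judge whether a larger trial is feasible. The closing paragraph of section 2 gives figures: "greater than 80% recruitment and retention of eligible participants, and greater than 90% adherence to the study protocol". That sentence opens with "By the completion of this pilot study, our expected outcomes are to have demonstrated a high level of procedural fidelity", so the figures are expectations for the end of the pilot. No formula, denominator or time window is given.

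Section 6 (Sample Size Determination) sets the sample at 20 patients, described as attainable in a planned period of one year. It supports this with two statements: "Our group treats approximately 35-40 patients per year who would likely meet inclusion criteria for this trial", and, of an assumed 200-patient randomised trial, "a 10% sample of that cohort will be sufficient provide preliminary safety data as well as to demonstrate feasibility of a future trial".

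Section 3.1 splits the 20 into two stages: "the first phase will include five patients treated and followed sequentially", then, if there is at most one major wound occurrence, "the second phase which will include a total of 15 patients followed concurrently". The interval between patients in the first stage is not stated.

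**The concern.** Placed next to each other, the figures seem to conflict. If 35-40 eligible patients come through in the year and only 20 can enter, the share recruited is little more than half, even if everyone who is asked agrees. The sequential first stage makes this worse, because eligible patients keep arriving while each of the first five is being followed.

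If that reading were correct, the pilot would miss one of its own feasibility expectations by construction. A reader might then judge the randomised trial infeasible for a reason unrelated to patients' willingness to take part. Alternatively, the denominator might be chosen once the results were known.

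**Working it through.** **Inputs from the protocol.** Sample 20 (5 + 15); pool 35-40 a year; period one year; assumed future trial 200; target above 80%.

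**Assumptions.** Patients arrive evenly. Each sequential patient takes 30 days (the primary endpoint window in section 3.2) or 90 days (the adverse event follow-up in section 7.1, counted there from discharge).

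1. *The plan's own figure.* 0.10 × 200 = 20, which reproduces the sample size. It is below 35-40, so the statement that 20 is attainable in a year agrees with the pool figure.

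2. *Denominator = everyone in the annual pool.* 20/40 = 50.0% and 20/35 = 57.1%. Since 0.8 × 35 = 28 and 0.8 × 40 = 32, exceeding 80% needs 29 or 33 patients, more than the 20 places. On this reading the target is out of reach.

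3. *Denominator = eligible patients offered an open place until 20 are enrolled.* 20/d exceeds 0.80 when d is below 25. So d = 24 gives 20/24 = 83.3%, while 20/25 = 80.0% does not exceed the target. Twenty-four patients present in 24/40 × 12 = 7.2 months to 24/35 × 12 = 8.2 months, before any sequential hold. On this reading the target is attainable.

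4. *Effect of exclusions.* The 35-40 are described as likely to meet the inclusion criteria. Section 4.2 then removes, among others, patients on chemotherapy, with earlier mesh repair, or with concurrent procedures. To bring the yearly eligible count down to 24, exclusions would have to remove 1 − 24/35 = 31% to 1 − 24/40 = 40%. The protocol does not give the actual share.

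5. *Sequential first stage, counting every arrival.*
   - At 30 days each, the stage lasts 5 × 30 = 150 days. Arrivals are 35 × 150/365 = 14.4 to 40 × 150/365 = 16.4, for 5 places. With full consent in stage 2 the ceiling is 20/(14.4 + 15) = 68% to 20/(16.4 + 15) = 64%.
   - At 90 days each (450 days), arrivals are 43.2 to 49.3 and the ceiling is 20/58.2 = 34% to 20/64.3 = 31%.
   - To exceed 80%, fewer than 10 patients could arrive in stage 1, since 20/(10 + 15) = 80%. That means less than 10/40 × 365/5 = 18 days to 10/35 × 365/5 = 21 days per patient.

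6. *Sequential first stage, counting only offers of an open place.* The hold does not enter the ratio; it only lengthens accrual. At 30 days each the hold is 150 days, about 4.9 months. Stage 2 at 20/24 consent needs 15 × 24/20 = 18 eligible patients, or 18/40 × 12 = 5.4 to 18/35 × 12 = 6.2 months. The total is 10.3 to 11.1 months. Average waits for each of the first five add 5 × 24/20 = 6 arrivals, or 1.8 to 2.1 months, giving 12.1 to 13.2 months. The share recruited is still 83.3%.

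The same 20 patients therefore give about 50% or above 80%, depending only on the denominator.

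**The case for a change.** The best case for a change rests on the literal wording. The target refers to eligible participants, not to those approached, and the only eligibility count in the protocol is 35-40 a year. On that reading the target and the sample size cannot both hold. Finishing early does not help unless each sequential patient takes less than about three weeks, which is shorter than the 30-day endpoint. No stated figure supports exclusions as large as 31-40%. Leaving the denominator open lets it be chosen after the data are seen, and a defining sentence would cost almost nothing.

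The arithmetic in this case stands, and so does the gap: recruitment has no stated denominator or window, and retention has no stated timepoint, although section 4.4.1 refers to 30 days and section 3.3 to two years.

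The inference of failure does not stand. It counts people for whom no place existed as failures to recruit, which no section asks for. It also treats a remark about attainability as a forecast of uptake. Nor does any decision depend on the percentage: the stage rule in section 3.1 concerns wound occurrences, and the stopping rules in section 7.4 concern safety. With 20 patients, the numbers eligible, offered and consented can simply be listed, so a reader can form either ratio.

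**Conclusion.** The concern does not hold as a contradiction. The 50-57% is correct arithmetic for a definition that the protocol does not state. On the reading that suits a pilot with a fixed number of places, consent among eligible patients offered entry, more than 80% is attainable (at least 20 of 24), and the sequential stage affects only the time taken. The ceilings of 64-68% and 31-34% depend on assumed intervals of 30 and 90 days and on counting patients who could not be offered a place.

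What remains is missing detail in a descriptive feasibility measure. An analyst would fill it by reporting consented over offered, giving separately the eligible patients who arrived when no place was open, and reporting retention by visit. Writing that down would leave the 80% target, the sample size and every decision in the pilot as they are, so no change is called for. This conclusion rests on the 80% being an expected outcome; it would be different if the figure were a formal criterion for going on to the randomised trial.

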Our long-term goal is to develop a technique for closure of ostomy sites that minimizes the potential for hernia formation. The current literature is limited by a lack of prospective evaluation of the effectiveness of reinforcement of ostomy closure sites. Therefore, prospectively evaluating the technique will yield a more detailed understanding of how and when hernia formation at the ostomy closure site occurs and the presence of any unexpected findings. Our overall objectives in this study protocol, which is the first step towards our long-term-goal, are to (i) validate our ostomy site closure technique incorporating prosthetic mesh and calculate its associated costs, (ii) measure and compare patient reported quality of life pre- and post-intervention, and (iii) prospectively evaluate the incidence of hernia at

the stoma closure site at 6-months post procedure. Our central hypothesis is that a mesh reinforcement of the site during closure of an ostomy is safe and will reduce the incidence of hernia over time. The rationale for this project is that survival from colorectal cancer will continue to increase and improving the quality of life of patients by reducing long term complications of surgical therapy can be achieved through improvements in technique.

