3.2 Primary Study Endpoints

The primary end point of the study is the validation of the mesh implantation procedure. We will assess the incidence of wound occurrences (defined as S-SSI, D-SSI, organ space SSI, dehiscence, and seroma formation) at 30days, with particular attention to wound occurrences requiring procedural intervention, including but not limited to, operative debridement, radiographically guided drain placement, or excision of the mesh. These incidences will be compared to historical controls.

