3.3 Secondary Study Endpoints

The secondary endpoints will be evaluation of the incidence of hernia formation at the ileostomy site on a prospective basis at 30 days and 6 month intervals thereafter until two years from the date of ileostomy closure. The Promis SF 2.0 8a Ability to Participate in Social Roles and Activities instrument will be used to assess quality of life and the Colorectal Functional Outcome (COREFO) instrument will be used to evaluate bowel function at each interval.

4 Subject Selection and Withdrawal

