6.3 Statistical Methods

The results of this study will be compared using a univariate analysis to historical control data obtained from the DHMC ACS-NSQIP database, with emphasis on surgical site occurrences including all types of SSI, and unplanned return to the operating room data points. The preliminary safety and feasibility data obtained from this study will be used to inform design of a larger study to test the hypothesis that the procedure can obtain a 50% reduction in the incidence of hernia formation at previous ileostomy sites compared to rates reported in the literature. The secondary objectives have not been previously reported in the literature either for patient reported outcomes or prospective evaluation of hernia formation. Further work, based on the data from this study, will attempt to show the superiority of the technique over currently used closure techniques as well as patient satisfaction with the procedure.

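### Section 2 expects to show quality of life similar to historical controls, but the plan identifies no historical quality-of-life comparator

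*Combined protocol and SAP*

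**What the plan says.** The last paragraph of Section 2 lists what the pilot is expected to have shown by its end. One item reads: "We also expect to preliminarily demonstrate safety and similar quality of life compared to historical controls on short term follow-up". The same paragraph says the results should inform a randomized trial.

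Historical controls appear in two other places:

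- Section 3.2, after defining the 30-day wound occurrences: "These incidences will be compared to historical controls".
- Section 6.3, which announces a univariate comparison with "historical control data obtained from the DHMC ACS-NSQIP database, with emphasis on surgical site occurrences including all types of SSI", and with "unplanned return to the operating room data points".

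Later in Section 6.3 the plan says: "The secondary objectives have not been previously reported in the literature either for patient reported outcomes or prospective evaluation of hernia formation".

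On measurement, Section 3.3 says: "The Promis SF 2.0 8a Ability to Participate in Social Roles and Activities instrument will be used to assess quality of life". COREFO is added for bowel function. Both are given at the Section 3.3 visits, which are 30 days and then every six months up to two years.

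Two further quality-of-life comparisons are stated. An overall objective in Section 1.1 is to "measure and compare patient reported quality of life pre- and post-intervention". Secondary Objective #1 in Section 2 is to "Measure and compare quality of life scores for aspects related to the procedure to those related to bowel function".

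**The concern.** A claim of similarity needs something to be similar to. The design has a single treated cohort, so the comparator for quality of life would have to come from outside it. The plan describes an outside source only for wound and reoperation outcomes, and its remark on the literature does not point to another.

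At stake is what the pilot may conclude. Section 2 hands its results to the design of a randomized trial, and Section 12 plans secondary publications on patient-reported outcomes. A statement that mesh closure leaves quality of life unchanged relative to standard closure could enter both without data behind it. Choosing a reference figure after the scores are known would be a poor remedy. Section 1.1 says quality of life after sphincter-sparing surgery varies widely and tracks how close the anastomosis lies to the anal canal, so the answer could depend on which reference was picked.

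**Working it through.** The plan gives no figure for this claim, so there is none to reproduce. The check sets the relevant texts side by side.

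**1. What the sentence needs.** To support it, the plan would need a historical group or reference value on the same instrument at a comparable short-term visit, an SD, and a margin that defines similar.

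**2. What the plan supplies.**

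| Requirement | Where one would look | What is there |
|---|---|---|
| Historical source | 6.3 | ACS-NSQIP, with emphasis on SSO, SSI and unplanned return to theatre; no quality-of-life item listed |
| Outcomes compared with history | 3.2 | Wound-occurrence incidences only |
| Literature value | 6.3 | Secondary objectives described as unreported for patient-reported outcomes |
| Scores from standard-closure patients | 3.1, 3.3, 5 | None planned |
| SD, margin, quality-of-life analysis | 6.1 to 6.4 | None |

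**3. Whether the other quality-of-life comparisons fill the gap.** The one in Section 1.1 is before versus after, within patients. Secondary Objective #1 sets one kind of score against another, also within patients. Neither involves historical controls. The before-versus-after comparison has a gap of its own: Section 3.3 starts at 30 days, and Section 5.1 (Encounter 1) mentions no questionnaire. Adding a baseline would close that gap but would still not supply a historical control.

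**4. Count.** The planned cohort is 5 + 15 = 20 (Section 3.1), which agrees with 10% × 200 = 20 (Section 6.1, under the paragraph numbered 6.2). Standard-closure patients with a planned PROMIS 8a or COREFO score: 0. Section 6.4 excludes patients without complete follow-up, so 20 is an upper limit.

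**5. Illustration: what 20 patients could show if a reference existed.** The documents give no SD, so results are in SD units. Two-sided 95% confidence, one-sided 2.5% and 80% power are my assumptions. The 16-patient case is 80% of 20, taking the retention figure in Section 2 as a lower case.

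- Half-width of the 95% CI for a mean = t(0.975, n − 1)/√n. For n = 20: 2.093/4.472 = 0.47 SD. For n = 16: 2.131/4 = 0.53 SD.
- Smallest non-inferiority margin against a fixed reference, true difference zero = (1.960 + 0.842)/√n. For n = 20: 2.802/4.472 = 0.63 SD. For n = 16: 2.802/4 = 0.70 SD.
- Against a historical group of assumed size m, with 20 mesh patients = 2.802 × √(1/20 + 1/m). For m = 40: 0.77 SD. For m = 200: 0.66 SD.

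Even with a comparator, the absence of a detectable difference would be weak evidence of similarity. The finding does not depend on this step.

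**The case against.** The strongest reply has four parts.

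- **The sentence is modest.** It is an expectation, hedged as preliminary, in a paragraph of anticipated outcomes. It is not an objective, an endpoint or a specified test. This stands, and it limits the importance of the point. It does not supply a comparator.
- **The list in Section 6.3 is not exhaustive.** The database is to be used with an emphasis on certain outcomes, and its full content is not described. Section 2 also does not say which historical controls it means. A reader might infer that no quality-of-life comparator exists anywhere, or that the database can hold only complications. The documents support neither. They show only that no such comparator is identified.
- **The literature sentence has a narrower reading.** It speaks of the secondary objectives, and the first of these is a particular comparison of procedure-related with bowel-function scores. A reader might infer that quality of life after standard closure has never been reported. The text does not say that, and Section 1.1 itself cites work on quality of life after sphincter-sparing surgery and with hernias. What remains is that the plan points to no published value it could use.
- **The claim is limited in time.** It concerns short-term follow-up. A reader might extend the failure to every visit up to two years, but Section 2 makes no such promise for the later visits.

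It could also be argued that the historical comparison was meant for safety alone. The wording attaches it to quality of life, and no other comparator is offered there.

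**Conclusion.** The concern holds in this form: Section 2 expects a conclusion of similar short-term quality of life against historical controls, and the plan identifies no historical quality-of-life source, reference value, margin or analysis to support it. As written, that conclusion cannot be drawn from the design and the data it names.

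The size is 0 standard-closure patients with a planned score against at most 20 mesh patients. This rests on reading the documents as they stand and on no assumed figure; the SD-unit margins are illustration only.

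The consequence is modest. The primary wound endpoint, the rule for moving to the second phase and the stopping rules are untouched. A reader might also infer that the pilot can say nothing useful about quality of life. That goes too far: within-cohort summaries remain possible, and so does a before-versus-after comparison if a pre-operative score is collected.

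**What to change.** - **Section 2, expected outcomes:** delete the clause on quality of life relative to historical controls. Limit the historical comparison to the outcomes Section 6.3 names: SSO, SSI and unplanned return to theatre.
- **Section 6.3:** add that PROMIS 8a and COREFO will be summarized within the mesh cohort by visit (mean, SD, completion rate) to help plan the randomized trial, and that no conclusion of similarity to standard closure will be drawn.
- **Sections 1.1, 2 and 3.3:** keep the before-versus-after comparison and the comparison of procedure-related with bowel-function scores, and reconcile both with the assessment schedule. Section 3.3 lists no pre-operative score, which the first of these needs.

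If the sponsor prefers to keep the historical claim, the alternative is to name, before scores are seen, a source with the same instrument and a comparable visit, a similarity margin, and how anastomosis height will be handled. The illustration above suggests that only a wide margin would be testable with 20 patients.

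The recommended route costs a few sentences and one secondary claim. If the before-versus-after objective is kept, it also needs one pre-operative questionnaire per patient.
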